9.2.2 Efficacy Endpoints

9.2.2.1 Primary Endpoint

Objective response rate (ORR) as defined by immune-related response criteria (irRC) will be the primary endpoint of the study. As mentioned, the primary hypothesis is that ORR of pembrolizumab in uveal melanoma will be 20%. We will enroll 10 patients in stage I to allow for early termination for futility. If no responses are observed the trial will be terminated. However, if ≥ 1 objective response occurs, OR if ≥ 2 patients experience stability of disease for ≥ 24 weeks, the trial will proceed to stage II.

Product: MK-3475

Protocol/Amendment No. 03

In stage II, an additional 19 patients will be enrolled. If ≥ 4 responses occur in all patients treated on stage I and stage II, the trial will be considered positive.

Of note, response rates by RECIST 1.1 criteria will also be assessed although irRC will be used for the primary endpoint.

ORR will be stratified by PD-L1 expression and *GNAQ/GNA11* mutation status (see section 8.2.2.3).

9.2.2.2 Secondary Endpoints

9.2.2.2.1 Progression Free Survival

Progression-free survival (PFS) as defined as the time from the first dose of pembrolizumab to progression as defined by RECIST 1.1 criteria. PFS will be summarized in the method of Kaplan and Meier. Median PFS and PFS at one year will be reported with 95% confidence intervals. PFS analysis based on investigator's assessment using irRC will also be carried out.

Since disease progression is assessed periodically, progressive disease (PD) can occur any time in the time interval between the last assessment where PD was not documented and the assessment when PD is documented. For the primary analysis, for the patients who have PD, the true date of disease progression will be approximated by the date of first assessment at which PD is objectively documented using RECIST 1.1 criteria, regardless of discontinuation of study drug. Death is always considered as a confirmed PD event. Patients without documented PD/death will be censored at the last disease assessment date.

9.2.2.2.2 Overall Survival

Overall survival is defined as the interval between the first dose of pembrolizumab and death for any reason. The Kaplan-Meier method will be used to estimate the overall survival. The treatment difference in survival will be assessed by the stratified log-rank test. Median survival and its 95% confidence interval will be estimated and reported.

9.2.2.2.3 Duration of Response

If sample size permits, response duration will be summarized descriptively using Kaplan-Meier medians and quartiles. Only the subset of patients who show a complete response or partial response will be included in this analysis.

9.2.2.3 Subgroup Analyses

To investigate predictors of response to pembrolizumab in uveal melanoma, we will stratify outcomes (ORR, PFS, OS) by clinical and laboratory factors. Clinical factors will include baseline LDH, visceral involvement, ECOG performance status, prior ipilimumab, and prior MEK inhibitor therapy. To investigate for possible genetic biomarkers for response, we will perform *GNAQ²⁰⁹/GNA11^{Q209}* mutation analysis and evaluate outcomes by mutation status. In addition, we will perform stratification by PD-L1 expression status.

Product: MK-3475

Protocol/Amendment No. 03

Differences in PFS and OS between subgroups will be assessed by the stratified logrank test. Differences in ORR between subgroups will be assessed by the Pearson chi-square test. No adjustments will be made for multiple comparisons.

9.2.3 Safety Endpoints

Adverse events attributed to pembrolizumab will be listed by CTCAE grade and reported in terms of the number of patients who experienced adverse events as a percentage of all treated patients. This endpoint will be reported descriptively without formal statistical analysis.

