3.2 Secondary Objective(s) & Hypothesis(es)

- (1) To evaluate progression-free survival (PFS) in patients with advanced uveal melanoma receiving pembrolizumab.
- (2) To evaluate safety, tolerability and adverse experience profile of pembrolizumab in uveal melanoma.
- (3) To evaluate overall survival (OS) in patients with advanced uveal melanoma receiving pembrolizumab.

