7.2 Assessing and Recording Adverse Events

An adverse event is defined as any untoward medical occurrence in a patient or clinical investigation subject administered a pharmaceutical product and which does not necessarily have to have a causal relationship with this treatment. An adverse event can therefore be any unfavorable and unintended sign (including an abnormal laboratory finding, for example), symptom, or disease temporally associated with the use of a medicinal product or protocol-specified procedure, whether or not considered related to the medicinal product or protocol-specified procedure. Any worsening (i.e., any clinically significant adverse change in frequency and/or intensity) of a preexisting condition that is temporally associated with the use of the Merck's product, is also an adverse event.

Changes resulting from normal growth and development that do not vary significantly in frequency or severity from expected levels are not to be considered adverse events. Examples of this may include, but are not limited to, teething, typical crying in infants and children and onset of menses or menopause occurring at a physiologically appropriate time.

Merck product includes any pharmaceutical product, biological product, device, diagnostic agent or protocol-specified procedure, whether investigational (including placebo or active comparator medication) or marketed, manufactured by, licensed by, provided by or distributed by Merck for human use.

Adverse events may occur during the course of the use of Merck product in clinical trials or within the follow-up period specified by the protocol, or prescribed in clinical practice, from overdose (whether accidental or intentional), from abuse and from withdrawal.

Adverse events may also occur in screened subjects during any pre-allocation baseline period as a result of a protocol-specified intervention, including washout or discontinuation of usual therapy, diet, placebo treatment or a procedure.

All adverse events will be recorded from the time the consent form is signed through 30 days following cessation of treatment and at each examination on the Adverse Event case report forms/worksheets. The reporting timeframe for adverse events meeting any serious criteria is described in section 7.2.3.1.

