7.2.3 Immediate Reporting of Adverse Events to the Sponsor and to Merck

7.2.3.1 Serious Adverse Events

A serious adverse event is any adverse event occurring at any dose or during any use of Merck’s product that:

- Results in death;
- Is life threatening;
- Results in persistent or significant disability/incapacity;
- Results in or prolongs an existing inpatient hospitalization;
- Is a congenital anomaly/birth defect;
- Is a new cancer (that is not a condition of the study);
- Is associated with an overdose;
- Is another important medical event

Progression of the cancer under study is not considered an adverse event unless it results in hospitalization or death.

Any serious adverse event, or follow up to a serious adverse event, including death due to any cause other than progression of the cancer under study that occurs to any subject from the time the consent is signed through 90 days following cessation of treatment, or the initiation of new anti-cancer therapy, whichever is earlier, whether or not related to Merck product, must be reported within 24 hours to the Sponsor and within 2 working days to [REDACTED]

Non-serious Events of Clinical Interest will be forwarded [REDACTED] handled in the same manner as SAEs.

Additionally, any serious adverse event, considered by an investigator who is a qualified physician to be related to Merck product that is brought to the attention of the investigator at any time outside of the time period specified in the previous paragraph also must be reported immediately to the Sponsor and to Merck.

A copy of all 15 Day Reports and Annual Progress Reports is submitted as required by FDA, European Union (EU), Pharmaceutical and Medical Devices agency (PMDA) or other local regulators. Investigators will cross reference this submission according to local regulations to the [REDACTED] the time of submission.

All subjects with serious adverse events must be followed up for outcome.

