Subjects should be assessed for possible ECIs prior to each dose. Lab results should be evaluated and subjects should be asked for signs and symptoms suggestive of an immune-related event. Subjects who develop an ECI thought to be immune-related should have additional testing to rule out other etiologic causes. If lab results or symptoms indicate a possible immune-related ECI, then additional testing should be performed to rule out other etiologic causes. If no other cause is found, then it is assumed to be immune-related.

ECIs that occur in any subject from the date of first dose through 90 days following cessation of treatment, or the initiation of a new anticancer therapy, whichever is earlier, whether or not related to the Merck’s product, must be reported within 24 hours to the Sponsor and to [REDACTED] within 2 working days.

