7.2.4 Evaluating Adverse Events

An investigator who is a qualified physician will evaluate all adverse events according to the NCI Common Terminology for Adverse Events (CTCAE), version 4.0. Any adverse event which changes CTCAE grade over the course of a given episode will have each change of grade recorded on the adverse event case report forms/worksheets.

All adverse events regardless of CTCAE grade must also be evaluated for seriousness.

Table 10 Evaluating Adverse Events

An investigator who is a qualified physician will evaluate all adverse events as to:

V4.0 CTCAE Grading	Grade 1	Mild; asymptomatic or mild symptoms; clinical or diagnostic observations only; intervention not indicated.
	Grade 2	Moderate; minimal, local or noninvasive intervention indicated; limiting age-appropriate instrumental ADL.
	Grade 3	Severe or medically significant but not immediately life-threatening; hospitalization or prolongation or hospitalization indicated; disabling; limiting self-care ADL.
	Grade 4	Life threatening consequences; urgent intervention indicated.
	Grade 5	Death related to AE
Seriousness	A serious adverse event is any adverse event occurring at any dose or during any use of Merck product that:	
	† Results in death; or	
	† Is life threatening; or places the subject, in the view of the investigator, at immediate risk of death from the event as it occurred (Note: This does not include an adverse event that, had it occurred in a more severe form, might have caused death.); or	
	† Results in a persistent or significant disability/incapacity (substantial disruption of one's ability to conduct normal life functions); or	
	† Results in or prolongs an existing inpatient hospitalization (hospitalization is defined as an inpatient admission, regardless of length of stay, even if the hospitalization is a precautionary measure for continued observation. (Note: Hospitalization [including hospitalization for an elective procedure] for a preexisting condition which has not worsened does not constitute a serious adverse event.); or	
	† Is a congenital anomaly/birth defect (in offspring of subject taking the product regardless of time to diagnosis); or	
	Is a new cancer; (that is not a condition of the study) or	

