	Likely Cause	Is the AE not reasonably explained by another etiology such as underlying disease, other drug(s)/vaccine(s), or other host or environmental factors

Relationship to Merck product (continued)		The following components are to be used to assess the relationship between the test drug and the AE: (continued)	
	Dechallenge	
Was the Merck product discontinued or dose/exposure/frequency reduced? If yes, did the AE resolve or improve? If yes, this is a positive dechallenge. If no, this is a negative dechallenge.
 
(Note: This criterion is not applicable if: (1) the AE resulted in death or permanent disability; (2) the AE resolved/improved despite continuation of the Merck product; or (3) the trial is a single-dose drug trial); or (4) Merck product(s) is/are only used one time.)
	
	Rechallenge	
Was the subject re-exposed to the Merck product in this study? If yes, did the AE recur or worsen? If yes, this is a positive rechallenge. If no, this is a negative rechallenge.
 
(Note: This criterion is not applicable if: (1) the initial AE resulted in death or permanent disability, or (2) the trial is a single-dose drug trial); or (3) Merck product(s) is/are used only one time).
 
NOTE: IF A RECHALLENGE IS PLANNED FOR AN ADVERSE EVENT WHICH WAS SERIOUS AND WHICH MAY HAVE BEEN CAUSED BY THE MERCK PRODUCT, OR IF REEXPOSURE TO THE MERCK PRODUCT POSES ADDITIONAL POTENTIAL SIGNIFICANT RISK TO THE SUBJECT, THEN THE RECHALLENGE MUST BE APPROVED IN ADVANCE BY THE U.S. CLINICAL MONITOR AS PER DOSE MODIFICATION GUIDELINES IN THE PROTOCOL.
	
	Consistency with Trial Treatment Profile	Is the clinical/pathological presentation of the AE consistent with previous knowledge regarding the Merck product or drug class pharmacology or toxicology?	
The assessment of relationship will be reported on the case report forms /worksheets by an investigator who is a qualified physician according to his/her best clinical judgment, including consideration of the above elements.			
Record one of the following		Use the following scale of criteria as guidance (not all criteria must be present to be indicative of a Merck product relationship).	
Yes, there is a reasonable possibility of Merck product relationship.		There is evidence of exposure to the Merck product. The temporal sequence of the AE onset relative to the administration of the Merck product is reasonable. The AE is more likely explained by the Merck product than by another cause.	

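### The SAP's only adverse event analysis covers events attributed to pembrolizumab; no table of all events regardless of attribution is planned beside it

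*Combined protocol and SAP*

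**What the plan says.** Section 9.2.3 is the only AE analysis in the SAP as it can be read: "Adverse events attributed to pembrolizumab will be listed by CTCAE grade and reported in terms of the number of patients who experienced adverse events". The denominator is every treated patient, and the summary is descriptive, with no formal test.

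The matching secondary objective in 3.2 is "To evaluate safety, tolerability and adverse experience profile of pembrolizumab in uveal melanoma". It is not limited to related events.

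Collection is wider than the planned table:

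- Section 7.2 defines an AE without requiring a causal link and states: "All adverse events will be recorded from the time the consent form is signed through 30 days following cessation of treatment".
- Section 7.2.3.1 collects SAEs from consent to 90 days after treatment stops, "or the initiation of new anti-cancer therapy, whichever is earlier, whether or not related to Merck product, must be reported within 24 hours".
- Section 7.2.3.2 covers "ECIs that occur in any subject from the date of first dose through 90 days following cessation of treatment", with the same cut-off at new anti-cancer therapy and again regardless of relation.
- Section 7.2.4 adds "Any adverse event which changes CTCAE grade over the course of a given episode will have each change of grade recorded", so worst grade can be derived.

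Attribution is governed by 7.2.4. A qualified physician investigator answers yes or no after weighing listed criteria such as exposure, timing and likely cause. Section 5.2.4 makes the trial open-label, and section 1.0 gives it no control.

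**The concern.** In an uncontrolled trial, the split between drug effect and disease effect rests on individual judgment, and no comparison arm exists to check it. If only the Yes events are tabulated, the reported AE rates move with those judgments, and the table gives no sign of how far.

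One of the attribution criteria asks: "Is the AE not reasonably explained by another etiology such as underlying disease". Table 1 in 5.1.3 admits patients with liver metastases whose AST and ALT are up to 5 x ULN. Hepatic events are therefore one place where drug and disease are hard to separate. The documents do not say how many patients this concerns.

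The protocol's own background uses both kinds of rate. Section 1.1 quotes grade 3 or 4 events overall and treatment-related. Section 4.2.2 quotes grade 3 or higher AEs and SAEs with no attribution filter stated, and discontinuations that were attributed to treatment. An attributed-only table could not be set against the unfiltered figures. If the all-cause table is left unplanned, whether to show it could also be decided after the data are seen.

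**Working it through.** **Step 1. Where would an event marked No appear?** The plan states no safety figure to reproduce, so the check starts by tracing such an event through section 9.

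| Event marked No | Planned output |
|---|---|
| Fatal | Counted in OS (9.2.2.2.2) and PFS (9.2.2.2.1), not in an AE table |
| Ends treatment | Counted under primary reason for discontinuation (9.2.4), not in an AE table |
| Any other, including a grade 3-4 event or SAE that neither ends treatment nor causes death | None |

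Pages after 9.2.4 are blacked out. The table of contents lists 9.2.4 as the last SAP subsection before section 10, so nothing suggests a further AE analysis behind the redaction.

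**Step 2. What one attribution call is worth.** The inputs are the two possible sample sizes in 2.2.1: 10 patients after stage 1 and 29 after stage 2. If a patient's only event of a given type is marked No instead of Yes, the rate falls by 1/n:

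- n=29: 1/29 = 3.4 percentage points
- n=10: 1/10 = 10 percentage points

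**Step 3. Illustration of how far two such tables can differ.** The only pair of overall and related rates for the same event type in the documents is for nivolumab, in 1.1: grade 3 or 4 AEs in 49% of patients, and treatment-related ones in 14%. That is another drug, at several doses and in several tumors. The documents give no such pair for pembrolizumab.

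The expected count is rate x n. The exact (Clopper-Pearson) 95% limits for x of n are the 0.025 quantile of Beta(x, n-x+1) and the 0.975 quantile of Beta(x+1, n-x).

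| | n=29, expected | Rounded to patients | Rate | Exact 95% CI | n=10, expected |
|---|---|---|---|---|---|
| All-cause | 0.49 x 29 = 14.2 | 14 | 48% | 29% to 67% | 4.9 |
| Attributed | 0.14 x 29 = 4.1 | 4 | 14% | 4% to 32% | 1.4 |

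Under these borrowed rates, about 10 of 29 patients with a grade 3 or 4 event (14 - 4 = 10) would be absent from the planned table. That gap includes events caused by the disease.

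**Step 4. Are the data there?** Section 7.2 says all AEs are recorded. Section 7.2.6 describes AE forms as documenting those of interest. An all-cause table can be built from existing data only if 7.2 governs.

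**The case against.** The strongest reply is that the objective concerns the profile of pembrolizumab, and drug-attributed events are a fair reading of that. The protocol's safety decisions use drug relation too: Table 3 in 5.2.1.2 covers drug-related events, and the safety criterion for early termination in 5.10 refers to adverse drug reactions. This stands as a defence of the attributed table. It does not explain why the remaining events, which the protocol collects, get no table.

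A second reply is that the percentage clause in 9.2.3 could be read as all-cause. That is grammatically possible but unnatural, since attribution to pembrolizumab qualifies the subject of the whole sentence. The section does not forbid an all-cause table, but it does not plan one either.

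Third, unattributed events are not lost. Section 7.2.5 sends all AEs to authorities, review boards and investigators under applicable law, and 7.2.3.1 refers to annual reports. The text of 11.4 on results posting is blacked out and may add more. This lessens the consequence but supplies no planned analysis.

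Fourth, attribution is structured. For a possible immune-related ECI, 7.2.3.2 says: "If no other cause is found, then it is assumed to be immune-related". That default reduces the problem for those events only.

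Finally, a reader might infer that the plan hides drug toxicity, and that the 49% against 14% contrast measures how much. The documents do not support this. The contrast comes from another drug and includes disease-related events. Nothing in the documents shows that attribution in this trial would be wrong, or in which direction.

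**Conclusion.** The concern holds as one of incompleteness. The attributed-only table in 9.2.3 is valid, but followed as written the SAP leaves some collected events without any summary: those marked No that neither end treatment nor cause death. It also makes the AE rates depend on unblinded, uncontrolled attribution.

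The certain part of the size is the one-patient step in the working. The nivolumab contrast shows only that the two tables can differ widely; it is not a forecast for this trial.

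It would go too far to say that 9.2.3 contradicts the safety objective or invalidates an analysis. Safety is a secondary, descriptive endpoint with no hypothesis or SAP decision rule attached. The primary endpoint, sample size, alpha and power are untouched. The conclusion assumes that the natural reading of 9.2.3 is the intended one and that the blacked-out pages hold no further AE analysis. The change should be made because the gap is specific and closing it costs little.

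**What to change.** Amend 9.2.3 to plan, for all treated patients:

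1. All AEs by worst CTCAE grade, regardless of attribution, from first dose through 30 days after cessation of treatment.
2. SAEs and ECIs, regardless of attribution, from first dose through 90 days after cessation or the start of new anti-cancer therapy, whichever is earlier.
3. The attributed events as now planned, kept as a second table.

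Apply these windows to the initial course and summarise second-course events (1.2, 7.1.6.2.2) separately; otherwise it is unclear which cessation date counts.

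Show deaths from progression of the cancer under study separately from other fatal SAEs. Section 7.2.3.1 says that progression resulting in death can be an AE, yet leaves deaths due to progression out of the SAE reporting clause. The two statements must be reconciled.

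Reconcile 7.2.6 with 7.2 by stating whether the AE forms capture all AEs. A listing of events between consent and first dose is optional. So is a progression flag, which would be an investigator judgment and may need a field that the protocol does not describe.

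The cost is one extra descriptive table set, a short SAP amendment and the clarifications in 7.2.6 and 7.2.3.1. No new data are needed if 7.2 governs collection. The downside is that all-cause rates will include disease-related events, which is why both tables should be shown.

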9.2.4 Baseline Characteristics and Other Analyses

Each relevant clinical characteristic will be recorded by the use of tables and/or graphs. No statistical hypothesis tests will be performed on these characteristics. The number and percentage of patients treated, and the primary reason for discontinuation will be displayed. Demographic variables (such as age) and baseline characteristics will be summarized by descriptive statistics.

Drug accountability data for pembrolizumab will be collected during the study. Compliance with pembrolizumab administration will be measured by patients: 1) receiving unscheduled study agent infusions/injections; 2) missing an infusion/injection. Numbers and percentages of patients and infusion/injection visits with any deviation in these measures will be reported.

[REDACTED]

[REDACTED]

[REDACTED]

[REDACTED]

[REDACTED]

[REDACTED]	[REDACTED]	[REDACTED]	[REDACTED]
[REDACTED]	[REDACTED]	[REDACTED]	[REDACTED]

[REDACTED]

[REDACTED]

[REDACTED]

[REDACTED]

Product: MK-3475

Protocol/Amendment No. 03

[REDACTED]

Product: MK-3475

Protocol/Amendment No. 03

[REDACTED]

Product: MK-3475

Protocol/Amendment No. 03

[REDACTED]

[REDACTED]

[REDACTED]

[REDACTED]

[REDACTED]

[REDACTED]

[REDACTED]

[REDACTED]

[REDACTED]

Product: MK-3475

Protocol/Amendment No. 03

[REDACTED]

[REDACTED]

[REDACTED]

[REDACTED]

[REDACTED]

[REDACTED]

.....

[REDACTED]

Product: MK-3475

Protocol/Amendment No. 03

A series of 12 horizontal black bars of varying lengths, decreasing from left to right. The bars are positioned on a white background and are evenly spaced vertically. The lengths of the bars decrease in a regular, linear fashion from the first bar on the left to the last bar on the right.

Protocol date: August 30, 2016

Product: MK-3475

Protocol/Amendment No. 03

[REDACTED]

Protocol date: August 30, 2016

[REDACTED]

[REDACTED]

[REDACTED]

[REDACTED]

